### **10.4.2. Efficacy failure**

Efficacy failure is defined as early treatment failure is first checked at week 6 post ATO. Treatment failure will be defined as:

- Required initiation of a new systemic treatment for chronic GvHD before week 6
- Recurrent or progressive malignancy before week 6
- Death before week 6

Failure-free survival (FFS), is defined as death, recurrent or progressive malignancy, or the initiation of a new systemic treatment for chronic GvHD (defined below).

From the perspective of the patient, secondary therapy and death have very different significance with respect to efficacy, since the need for secondary therapy does not inevitably lead to death. From the perspective of the clinical trial, however, both events indicate that the study-drug did not have the desired efficacy.

Discontinuation of treatment with study-drug because of toxicity will not be categorized as efficacy failure in and of itself, since it is possible that a short period of treatment with the study-drug could have long lasting benefit ultimately resulting in efficacy success. After a toxic study-drug outcome, patients will be followed for any subsequent initiation of secondary systemic treatment development of recurrent malignancy, death from causes other than recurrent malignancy, or dropout with lack of follow-up information. Any of these events occurring during primary treatment for chronic GvHD will be categorized as efficacy failure.

#### **10.4.3. Secondary systemic therapy**

Secondary systemic therapy includes any intervention intended to control chronic GvHD through an immunosuppressive effect from oral or parenteral administration of any systemic medication not originally given under auspices of this protocol. Examples include, but are not limited to the following: azathioprine, rapamycin, infliximab, daclizumab, etanercept, antithymocyte globulin, thalidomide, chloroquine, clofazimine, extracorporeal photopheresis, and psoralen with UVA irradiation.

Topical therapy, including glucocorticoid creams, topical tacrolimus, oral beclomethasone or budesonide, topical azathioprine and ophthalmic glucocorticoids, is not considered as secondary systemic therapy.

An increase in the dose of prednisone and any resumption of treatment with prednisone or study-drug after previous discontinuation for any reason is not considered as secondary systemic therapy. Any increase in the dose of ciclosporine or resumption of treatment with ciclosporine after previous discontinuation for any reason is not considered as secondary systemic treatment, if the drug in question was included in the immunosuppressive regimen when treatment for chronic GvHD was started.

A change in treatment from ciclosporine to tacrolimus because of drug toxicity is not considered as secondary treatment. This information must be reported in the electronic CRF of the study.

#### **10.4.4. Recurrent malignancy**

For purposes of this study, recurrent malignancy after allo-SCT is defined as clinical or histopathologic evidence demonstrating the presence of any malignancy considered as the indication for transplant. Recurrent malignancy after allo-SCT will also be defined as any post-transplant intervention not routinely used to prevent the development of overt recurrence, prompted by laboratory evidence of persisting malignant cells but without clinical or histopathologic evidence of recurrence. Recurrent malignancy after a non- myeloablative or reduced intensity conditioning regimen will be defined as any ad hoc post- transplant intervention intended to induce a donor immune-mediated anti-neoplastic effect, prompted by clinical or laboratory evidence indicating the need to eliminate persistent or progressive malignancy. Examples of such interventions include accelerated withdrawal of systemic immunosuppressive medications and donor lymphocyte infusion.

### **10.5. Missing data handling**

Every effort will be made to keep the number of missing values for all parameters to a minimum. Missing data on overall survival is assumed to be 0 as patient care after transplantation is very close.

### **10.6. Early stopping rules**

Experience acquired with the use of ATO in various clinical situations does not suggest a significant risk of study drug-related severe toxicities. Therefore, for the purpose of this study, no criterion for early stopping will be defined in advance.

### **10.7. Calculation of the number of patients**

Based on results from the literature, the hypothesis for the primary endpoint is an improvement in response rate (CR and PR) at 6 months after the diagnosis of chronic GvHD and start of ATO from 60% to 85%. Using a one-step A'Hern procedure (A'Hern RP, 2001) (and anticipating a dropout rate around 10%), 24 (21+3) patients are needed. If the number of successful cases is 17 or more among the 21 patients, the hypothesis that the CR rate at 6 months is less than 60% is rejected with a target error rate of 0.05 (alpha probability). The beta probability in this case is 0.2.

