### **10.2. Analyses data set**

Every patient included in the study and who has received at least one infusion of ATO will be taken into account at time of data analysis.

Patients who do not receive any injection of ATO will not be analyzed and will be replaced to obtain 24 patients provided in the statistical analysis.

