12.4.3.5 Determination of sample size

The aim of this study is to assess whether ATO allows improving response rate at 6 months after the diagnosis of chronic GVHD from 60% to 85%.

For the sample size calculation in this trial, an A'Hern one stage design has been used (ref 1).

- Let P_0 be the smallest response rate, if true, implies that the role of ATO is too low and therefore the present schedule does not warrant further investigation. In the present trial, P_0 has been taken as 60%.
- Let P_1 be the highest response rate which, if true, implies that the feasibility is sufficiently high and therefore the current schedule warrants further investigation in clinical trials. In the present trial, P_1 has been taken as 85%;
- Let α be the accepted probability of recommending for further investigation a regimen with a true discontinuation rate at least equal to P_0 . In the present trial, α has been taken as 0.05.
- Let β be the accepted probability of rejecting for further investigation a regimen with a true discontinuation rate less than P_1 . In the present trial, β has been taken as 0.20.

The required number of eligible patients is 21. To compensate for a dropout of 10%, 24 patients are planned to be included.

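### The responder cut-off of 17 is defined only for 21 patients, the protocol analyses 24, and the SAP's confidence-interval rule gives different thresholds

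*Protocol*

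**What the plan says.** Protocol 10.7, repeated in both synopses, sets the primary hypothesis on the response rate, CR and PR together, rising from 60% to 85%. It sizes the trial by a single-stage exact design ("Using a one-step A'Hern procedure"). The decision rule is a count, and what it rejects is a rate under 60%: "If the number of successful cases is 17 or more among the 21 patients, the hypothesis that the CR rate at 6 months". The target alpha is 0.05, with beta 0.2. Three patients are added for about 10% dropout, giving 24.

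Protocol 10.2 takes into the analysis every included patient with at least one infusion. Untreated patients "will be replaced to obtain 24 patients provided in the statistical analysis".

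SAP 12.4.3.5 keeps both numbers ("The required number of eligible patients is 21. To compensate for a dropout of 10%, 24 patients are planned to be included") but gives no cut-off. It defines P0 and P1 as response rates, then defines alpha through "a regimen with a true discontinuation rate at least equal to" P0, and beta through such a rate below P1.

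SAP 11.4.1.1 tests CR or PR in the FAS by comparing the lower limit of a 95% Clopper-Pearson interval with 60%. H0 is to be rejected when that limit is lower than 60%. SAP 11.1 limits the FAS to patients who completed the first cycle and had a Week 6 response evaluation.

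**The concern.** The three added patients make sense if dropouts leave the denominator and about 21 remain. Protocol 10.2 does the opposite: a treated patient who drops out is still analysed, and an untreated one is replaced. The protocol's own analysis set is therefore 24, while its success count and error rates belong to 21.

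This is the go/no-go decision of a single-arm trial, and the possible thresholds lie only one to three responders apart. An analyst with 22 to 24 patients has no count rule and might carry 17 over. An analyst following the SAP has an interval rule that is reversed as printed and stricter than the protocol when read as intended. The same data could count as success under one document and failure under the other.

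The hypotheses are also mislabelled. The count rule rejects a statement about CR although the endpoint is CR+PR. The SAP's alpha and beta refer to discontinuation, with inequalities that suit an unfavourable outcome and are reversed for a response rate.

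**Working it through.** **Inputs.** p0 = 0.60, p1 = 0.85, n = 21, r = 17, alpha 0.05, beta 0.20, dropout 10%, N = 24 (Protocol 10.7); 24 analysed (Protocol 10.2); two-sided 95% Clopper-Pearson limit against 60% (SAP 11.4.1.1). Sidedness of alpha is not stated; the single-stage exact count rule is one-sided by construction.

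**Formulas.** For X ~ Binomial(n, p), alpha = P(X ≥ r | 0.60) and power = P(X ≥ r | 0.85). The Clopper-Pearson lower limit is the q-quantile of Beta(r, n − r + 1), with q = 0.025 for the two-sided 95% interval and q = 0.05 for a one-sided 95% bound.

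**Step 1: the plan's own figure.** For r = 17, n = 21: alpha = 0.0370, power = 0.8025. A search over n shows that 21 is the smallest size meeting both targets. 21 / 0.90 = 23.3, rounded up to 24. The stated design reproduces.

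**Step 2: keep 17, let n grow.**

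| n analysed | alpha with r = 17 |
|---|---|
| 21 | 0.037 |
| 22 | 0.072 |
| 23 | 0.124 |
| 24 | 0.192 |

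**Step 3: smallest r with one-sided alpha ≤ 0.05, and both lower limits at that r.**

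| n | r | alpha | power | two-sided 95% lower limit | one-sided 95% lower limit |
|---|---|---|---|---|---|
| 21 | 17 | 0.037 | 0.803 | 0.581 | 0.616 |
| 22 | 18 | 0.027 | 0.774 | 0.597 | 0.631 |
| 23 | 19 | 0.019 | 0.744 | 0.612 | 0.645 |
| 24 | 19 | 0.040 | 0.861 | 0.578 | 0.611 |

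At n = 24, r = 18 would give alpha 0.096.

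**Step 4: the SAP rule.** As printed, a limit below 60% rejects H0, so 20 of 24 (limit 0.626) would not count as success while weaker results would. Read as intended (limit above 60%), it needs 18 of 21 (alpha 0.011, power 0.611) or 20 of 24 (alpha 0.013, power 0.713). It does not reject at 17 of 21, 18 of 22 or 19 of 24. The one-sided 95% limit exceeds 0.60 at every r in the Step 3 table, so it reproduces the count cut-offs.

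**Step 5: a dropout scenario, not a plan figure.** If 10% drop out independently and all count as failures, the success probability is 0.85 × 0.90 = 0.765 and P(X ≥ 19 | n = 24, p = 0.765) = 0.49.

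**The case against.** The strongest reply is that the plan is not without a rule. SAP 11.4.1.1 works at any n and tests CR or PR. The FAS can lose treated patients, so 21 evaluable patients can arise and the allowance of three is coherent with that set. This stands against any reading in which 17 of 21 is the only success criterion or 21 can never occur. It does not rescue the plan: the SAP rule is printed backwards, disagrees with 17 of 21 once corrected, falls short of 80% power at both 21 and 24, and uses a set that Protocol 10.2 does not define.

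Four stronger readings are tempting and not supported:
- **The trial runs at a 19% type I error.** No section tells anyone to apply 17 to 24. The rule is undefined there, and 0.192 is what carrying it over would produce.
- **The power is really about 0.49.** This counts every dropout as failure. The sentence in Protocol 10.4.2 that lists "death from causes other than recurrent malignancy, or dropout with lack of follow-up information" as failure concerns patients followed after a toxic outcome. Protocol 10.4.1 keeps as successes those lost after responding. SAP 12.4.3.2 uses the most plausible outcome for missing M6 data and leaves missing-as-failure to sensitivity analysis.
- **A positive result would be a claim about complete remission.** The same paragraph of Protocol 10.7 sets the hypothesis on CR and PR, and SAP 11.4.1.1 tests CR or PR. This is a wrong label.
- **The sample size is wrong.** The design for 21 reproduces, and 24 patients are enough for a valid rule.

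**Conclusion.** The point holds in this form: the plan's only responder-count rule belongs to 21 patients, so the stated alpha and beta do not describe the 24-patient set that Protocol 10.2 analyses, and the SAP's interval rule is a second, conflicting criterion. With 24 analysed, 19 responders are needed to hold one-sided alpha at 0.05 (0.040, power 0.861), two more than the printed 17. The SAP rule as intended needs 20 (power 0.713).

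These figures assume a one-sided 0.05 test, independent patients, and an M6 outcome assigned to everyone in the denominator. The label errors in Protocol 10.7 and SAP 12.4.3.5 do not alter the arithmetic but leave the formal hypotheses misstated. Because the threshold carries the trial's primary conclusion, it should be corrected before the data are read.

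**What to change.** State one analysis set and one decision rule in Protocol 10.7, SAP 12.4.3.5 and SAP 11.4.1.1, and carry the change into both synopses.

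- **Rule.** With 24 treated patients analysed, reject H0 (CR+PR rate at or below 60%) if at least 19 respond: exact one-sided alpha 0.040, power 0.861 at 85%.
- **Other n.** Use the smallest r with exact one-sided alpha at or below 0.05, and state the power: 17 of 21 (0.803), 18 of 22 (0.774), 19 of 23 (0.744). If a set that can fall below 21 is kept, extend the list: 17 of 20, for example, has alpha 0.016 and power 0.648.
- **SAP 11.4.1.1.** Require the one-sided 95% Clopper-Pearson lower bound (the lower limit of the two-sided 90% interval) to be above 60%. This gives the same cut-offs. Adding the counts while leaving the two-sided rule in place would keep two rules that disagree at 17 of 21, 18 of 22 and 19 of 24.
- **Analysis set.** Reconcile the FAS in SAP 11.1 with Protocol 10.2.
- **Labels.** Replace the CR rate by the CR+PR response rate, and the discontinuation rate by the response rate, with alpha defined at or below P0 and beta at or above P1.
- **Dropout.** If a scenario is shown, give 0.49 at 19 of 24 only as a pessimistic bound, with its assumption stated.

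The cost is wording in two documents and openly stated power below 80% at 22 or 23 patients. No extra patients are needed.

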## **11. Safety Management**

### **11.1. Adverse Events**

The following definitions and explanations are given to enable investigators and study nurses to correctly record, report and review adverse events (AEs) in order to comply with the safety requirements according to Good Clinical Practice (GCP) standards and the local and European requirements.

For all AEs, the investigator must pursue and obtain information adequate both to determine the outcome of the AE and to assess whether it meets the criteria for classification as a serious AE (SAE) (see Section 11.3.3) requiring immediate notification to Sponsor. For all AEs, sufficient information should be obtained by the investigator to determine the causality of the AE. The investigator is required to assess causality. For AEs with a causal relationship to the investigational medicinal product, follow-up by the investigator is required until the event or its sequelae resolve or stabilize at a level acceptable to the investigator, and Sponsor concurs with that assessment.

### **11.2. Reporting Period**

SAEs require immediate notification to Sponsor beginning from the time that the subject provides informed consent, which is obtained prior to the subject's participation in the clinical trial, i.e., prior to undergoing any trial-related procedure and/or receiving investigational medicinal product, through 30 days after the administration of the last dose.

Any SAE occurring any time after the reporting period must be promptly reported if a causal relationship to investigational medicinal product is suspected.

AEs (serious and non-serious) should be recorded on the electronic CRF from the time the subject has taken at least one dose of trial treatment through last subject visit.

## **11.3. Definitions**

### **11.3.1. Definition of an AE**

An AE is any untoward medical occurrence in a clinical investigation subject administered an investigational medicinal product; the event do not need necessarily have a causal relationship with the treatment or usage.

Examples of AEs include but are not limited to:

- Abnormal test findings;
- Clinically significant symptoms and signs;
- Changes in physical examination findings.

Additionally, they may include the signs or symptoms resulting from:

- Drug overdose;
- Drug abuse;
- Drug misuse;
- Medication error;
- Drug interactions;
- Exposure in utero.

Worsening of signs and symptoms of the cGVHD should not be reported as AEs in the appropriate section of the electronic CRF. PD is defined as at least one organ system has worsened by at least one stage without improvement of any other organ systems from baseline.

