  - For joint/fascia, a worsening of 1 point or more on the 0 to 3 scale is considered progression, even if from 0 to 1, because a change to score 1 was considered meaningful progression that would prompt a change in therapy. For joints assessed by the photographic range of motion, a worsening of 1 or more points for the 7-point scales and 1 or more points for the 4-point scale is considered progression.
  - For mouth, a worsening of 2 or more points on the 1-point scale indicates

progression.

- Worsening of liver GvHD is defined by an increase of 2 or more times the upper limit of normal for the assay for alanine transaminase, alkaline phosphatase, or total bilirubin.
- For patients with lung involvement, absolute worsening of FEV1 by 10% predicted or more (eg, 50% to 40%) is considered progression, as long as the final %FEV1 is < 65% (because initial %FEV1 must be < 75% to establish the diagnosis of lung involvement). If PFTs are not available, then worsening of the clinical lung score based on symptoms by 1 or more points should be scored as progression, except from score 0 to 1, which is considered trivial progression because of its lack of specificity for lung chronic GvHD.
- Mixed response is defined as CR or PR in at least one organ accompanied by progression in another organ
- Unchanged: outcome that do not meet criteria for CR, PR, PF or mixed response are considered unchanged

Response determination for chronic GvHD is indicated in the table below:

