### **9.3. Response criteria**

- Numbering of weeks/timing of events

Week 1 is the week corresponding to the first infusion of ATO. Weeks are counted from this week onwards, unless stated to the contrary. Investigators should take care not to confuse weeks post-ATO with weeks post-transplantation.

➤ Response to the study regimens:

- Assessment of response (CR vs. PR): The main issue in chronic GvHD is the lack of consensus criteria for the assessment of the response. In 2015 an NIH sponsored meeting was held with a panel of experts on chronic GvHD. Their proposal for grading of chronic GvHD will be used in this protocol (see Appendix 1).
- The following definitions will be used:
- Complete remission (CR) is defined as complete disappearance of any sign of chronic GvHD
- Partial remission (PR) is defined as improvement of 1 or more point on a 4 to 7-point scale or an improvement of 2 or more points on a 10 to 12-points scale in at least 1 organ or site without progression in any other organ or site. For patients with BOS, an absolute improvement in %FEV1 of 10% predicted or more (eg, 50% to 60%) is considered a PR as long as the initial % FEV1 is < 70%. Normalization ( $\geq 80\%$ ) is considered a CR.
- Progressive disease (PD) is defined as at least one organ system has worsened by at least one stage without improvement of any other organ systems from baseline
- For skin, eye, esophagus, and upper and lower GI tract, a worsening of 1 point or more on the 0 to 3 scale is considered progression, except a change from 0 to 1, which is considered trivial progression since it often reflects mild, nonspecific, intermittent, self-limited symptoms and signs that do not warrant a change of therapy.
- For joint/fascia, a worsening of 1 point or more on the 0 to 3 scale is considered progression, even if from 0 to 1, because a change to score 1 was considered meaningful progression that would prompt a change in therapy. For joints assessed by the photographic range of motion, a worsening of 1 or more points for the 7-point scales and 1 or more points for the 4-point scale is considered progression.

- For mouth, a worsening of 2 or more points on the 1-point scale indicates progression.
- Worsening of liver GvHD is defined by an increase of 2 or more times the upper limit of normal for the assay for alanine transaminase, alkaline phosphatase, or total bilirubin.

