### **11.3.2. Abnormal Test Findings**

The criteria for determining whether an abnormal objective test finding should be reported as an AE are as follows:

- Test result is associated with accompanying symptoms, and/or
- Test result requires additional diagnostic testing or medical/surgical intervention, and/or
- Test result leads to a change in trial dosing (*outside of protocol-stipulated dose adjustments*) or discontinuation from the trial, significant additional concomitant drug treatment, or other therapy, and/or
- Test result is considered to be an AE by the investigator or sponsor.

Merely repeating an abnormal test, in the absence of any of the above conditions, does not constitute an AE. Any abnormal test result that is determined to be an error does not require reporting as an AE.

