### **11.3.3. Definition of a Serious Adverse Event**

A SAE or serious adverse drug reaction is any untoward medical occurrence at any dose that:

- Results in death;
- Is life-threatening (immediate risk of death);
- Requires inpatient hospitalization or prolongation of existing hospitalization for medical reasons (e.g. prolongation of hospitalization for social reasons is excluded);
- Results in persistent or significant disability/incapacity;
- Results in congenital anomaly/birth defect.

Progression of the cGVHD (including signs and symptoms of progression) should not be reported as a SAE unless the outcome is fatal during the trial or within the safety reporting period. Hospitalization due to signs and symptoms of disease progression should not be reported as SAE.

Medical and scientific judgment should be exercised in determining whether an event is an important medical event. An important medical event may not be immediately life-threatening and/or result in death or hospitalization. However, if it is determined that the event may jeopardize the subject and/or may require intervention to prevent one of the other outcomes listed in the definition above, the important medical event should be reported as serious.

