**Table 5. Upper Limits (98%, in msec) of Normal QTc for Framingham formula (Luo S, 2004)**

Heart Rate (HR)	MALE (5,420)	FEMALE (4,883)	BOTH (10,303)
All HR	454	461	457
HR < 60	455	463	459
HR 60 to 99	454	462	458
HR > 99	436	434	436

For increased accuracy, the QT interval should be measured on serial EKGs and several successive beats and averaged for each EKG. The averaged QT value obtained should be used in the above formula in which all measurement must be expressed in msec (i.e.: 0,500 sec=500 msec). Applying this formula, a QTc interval > 500 msec must be considered prolonged (Summary of Product Characteristics (Trisenox)).

- Related to hepatotoxicity: increase in serum bilirubin and/or SGOT and/or SGPT and/or alkaline phosphatase,
- Related to Hematological toxicity. This drug may induce severe and prolonged myelosuppression with subsequent anemia, neutropenia, thrombocytopenia. Less frequently hyperleucocytosis or leucopenia have been reported.
- Related to general tolerance (fever, chills, fatigue, bleeding, edema...)
- Related to immunosuppression such as infectious complications (candidosis, herpes-zoster, pneumonia, bacteremia, septicemia, septic choc...),
- Related to digestive toxicity (nausea, vomiting, diarrhea...),
- Related to metabolism disorders (hyperglycemia, hypokalemia, hypomagnesaemia...),
- Renal insufficiency,
- Related to nervous system (paraesthesia, dizziness, headache...),
- Related to eye disorder (vision blurred),
- Related to cutaneous tissues (prurit, rash...),
- Related to musculoskeletal, connective tissue and bone disorders (myalgia, arthralgia, bone pain...).
- Related to pulmonary disorders (dyspnea,,,)

All AE not previously described in the Summary of Product Characteristics of TRISENOX® or in the Investigator Brochure of ARSCIMED® should be considered as unexpected AE.

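### SAP 12.2 summarises no liver test from the infusion weeks, when ATO liver toxicity is most likely to show; one worst-value table per cycle would close the gap

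*Protocol*

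**What the plan says.** **Laboratory schedule and summary.** Protocol 8.2 requires ALT (SGPT) and AST (SGOT) twice a week, and alkaline phosphatase (ALP) and bilirubin weekly, during each ATO cycle. SAP 12.2 describes each laboratory parameter at baseline, W6, W14, M6, M9 and M12. Protocol 8.1 postpones W6 and W14 where needed so that they stay two weeks after the end of a cycle. SAP 12.4.3.1 has all data listed in general, and listing 16.2.6.2 covers laboratory results.

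**AE and SAE rules.** Protocol 11.3.1 states: "Worsening of signs and symptoms of the cGVHD should not be reported as AEs in the appropriate section of the electronic CRF". Protocol 11.3.3 exempts non-fatal cGvHD progression from SAE reporting and adds: "Hospitalization due to signs and symptoms of disease progression should not be reported as SAE". Neither section makes an exception for a suspected ATO contribution. Protocol 11.2 does use suspicion as a trigger, but for SAEs after the reporting period, which "must be promptly reported if a causal relationship to investigational medicinal product is suspected". Protocol 11.3.2 makes an abnormal test reportable on several grounds, among them "Test result requires additional diagnostic testing or medical/surgical intervention" and "Test result is considered to be an AE by the investigator or sponsor". No text says how 11.3.2 and the exemption fit together.

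**Shared markers.** Protocol 7.3.2.1 says: "Worsening of liver GvHD is defined by an increase of 2 or more times the upper limit of normal". Section 9.3 repeats the rule "for the assay for alanine transaminase, alkaline phosphatase, or total bilirubin". Protocol 11.8 lists among the frequent ATO events: "Related to hepatotoxicity: increase in serum bilirubin and/or SGOT and/or SGPT and/or alkaline phosphatase".

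**The concern.** The trial has a single arm, so its safety case rests on the observed AE rates with their 95% confidence intervals and on the laboratory summaries. A liver rise that begins and ends around the infusions can be missing from both. It is absent from the laboratory summary because no summarised visit lies in the exposure window. It can be absent from the AE tables if the site files it as cGvHD worsening. Causality grading, and the rule in Protocol 11.5 that handles unknown causality as related, apply only once an event has been recorded as an AE. A rise of uncertain cause that is labelled cGvHD reaches neither step.

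**Working it through.** The plan states no figure on this point, so there is none to reproduce. The check is a calendar count and a comparison of rules.

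**1. Do any summary visits fall in an infusion week?** Example infusion days are 1-5, 8, 10, 12, 15, 17 and 24, which is weeks 1-4 (Protocol 5.1, SAP 9.3.3). Cycle 2 starts s = 8 to 11 weeks after the first infusion, so its first day is 1 + 7s and its last infusion day is 24 + 7s. The W6 or W14 visit comes at least 14 days after the last infusion.

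| Cycle | First day | Last infusion | Last infusion + 14 | Nominal visit day |
|---|---|---|---|---|
| 1 | 1 | 24 | 38 | W6 = 42 |
| 2, s = 8 | 57 | 80 | 94 | W14 = 98 |
| 2, s = 9 | 64 | 87 | 101 | W14 = 98, postponed |
| 2, s = 11 | 78 | 101 | 115 | W14 = 98, postponed |

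Even with the 5-day tolerance used in full, a visit falls 14 - 5 = 9 days after the last infusion. Baseline precedes ATO, and M6, M9 and M12 come later still. Result: 0 of the 6 time points lies in an infusion week. SAP 11.4.2.5, which also describes bilirubin, ALT and ALP, uses W6, W14, M6, M9 and M12, so it does not fill the gap.

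**2. How much is left unsummarised?** Per patient and cycle: ALT 2 x 4 = 8, AST 2 x 4 = 8, ALP 4, bilirubin 4; total 24. For 24 patients that is 24 x 24 = 576 values with one cycle each. The ceiling with two cycles each is 1,152, but only partial responders may have a second cycle, so it will not be reached in practice. If the four day 1 values are pre-dose, the figures are 20 x 24 = 480 and 960. These counts measure schedule volume, not bias.

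**3. Where do the two liver definitions overlap?**

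| Marker | Liver cGvHD worsening (7.3.2.1, 9.3) | ATO hepatotoxicity (11.8) |
|---|---|---|
| ALT | yes | yes |
| ALP | yes | yes |
| Bilirubin | yes | yes |
| AST | no | yes |

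Three of the four hepatotoxicity markers also define cGvHD worsening. If the exemption follows that definition, smaller rises (below the 2 x ULN criterion) and isolated AST rises fall outside it.

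**4. Illustrations only.** Suppose onset is spread evenly over days 1-24 and a rise lasts D days. The share still raised on visit day w is max(0, 24 - (w - D))/23.

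| D (days) | w = 33 | w = 38 | w = 42 |
|---|---|---|---|
| 7 | 0% | 0% | 0% |
| 14 | 5/23 = 22% | 0% | 0% |
| 21 | 12/23 = 52% | 7/23 = 30% | 3/23 = 13% |
| 28 | 19/23 = 83% | 14/23 = 61% | 10/23 = 43% |

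One omitted patient among 24 moves a rate by 1/24 = 4.2 points. With exact (Clopper-Pearson) 95% intervals, 1/24 (4.2%; 0.1-21.1%) becomes 0/24 (0-14.2%), and 3/24 (12.5%; 2.7-32.4%) becomes 2/24 (8.3%; 1.0-27.0%). Onset, duration and event counts are assumptions; the documents give none of them.

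**The case against.** The case on the other side is substantial, and most of it stands.

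- The exemption covers worsening of cGvHD, not ATO toxicity. A rise that the investigator attributes to ATO lies outside its words, SAP 12.1 has treatment-related toxicities recorded, and 11.3.2 makes many rises reportable in any case. A reader might infer that the protocol removes ATO hepatotoxicity from the AE data; the documents do not support that. What they leave unaddressed is mixed or uncertain cause.
- Form A has a field for an abnormality wholly explained by a non-GvHD cause, and the SAP tabulates it for the liver from W6 to M12. It does not cover mixed cause or the infusion weeks.
- A reader might infer that treatment interruptions leave no trace, because SAP 11.3.1 codes temporary discontinuation as yes or no, and an infusion cancelled and later given could read as no. The same section provides a discontinuation listing and tabulates infusions, dosing days and daily dose by week. Table 2 of the protocol collects the reason for a dose change. A delay or a half-dose restart can therefore be seen.
- Table 14.4.1.1 summarises AEs during treatment, the AE listing gives grade, causality and action taken, and an independent safety committee reviews the data (Protocol 11.9). With 24 patients, a laboratory listing can be read.
- A reader might also argue that W6 and W14 show recovered values because ATO restarts only after recovery. That rule (Protocol 7.3.2, dose delay) applies to grade 3 or greater toxicity judged possibly related to ATO, and such events have already been considered for causality. It gives no reason to expect recovery of rises below grade 3.

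None of these outputs summarises the infusion-week liver values, and none sets them against what was recorded as an AE.

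**Conclusion.** The point holds as a gap in the laboratory summary. The SAP 12.2 time points miss the exposure window for every patient, by design of the visit calendar, and this needs no assumption beyond the schedule being followed. The reporting exemption makes the gap matter more, because it leaves room for liver rises of mixed or uncertain cause, mainly below grade 3, to be filed as cGvHD and so to be absent from the AE tables too. How many such rises there would be cannot be derived from the documents. The duration shares and interval shifts above show what could happen and are not estimates. No endpoint, test or error rate changes. This is an inexpensive improvement to the safety reporting, not a defect that undermines the trial.

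**What to change.** Add one table to SAP 12.2 giving each patient's worst ALT, AST, ALP and bilirubin, as multiples of ULN, per cycle. The window runs from the first infusion of the cycle to the W6 visit (cycle 1) or the W14 visit (cycle 2). Count patients with ALT, AST or ALP at or above 3 and 5 x ULN, and with bilirubin above ULN and above 3 mg/dL. The ALT, ALP and bilirubin cut-offs are those already in SAP 11.2.3; AST would take the same ones. Include a column for whether a liver AE was recorded in the same period (yes/no), so that unmatched rises can be counted.

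The cost is a little programming, with no new visits or tests. The liver safety picture may look slightly less favourable.

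Optional, and only if enrolment is still open: limit the exemption in Protocol 11.3.1 and 11.3.3 to worsening for which an ATO contribution is judged not related or unlikely. This must go to the ethics committee and authorities (Protocol 13.1), and some disease worsening would enter the AE counts. I would not also give 11.3.2 general precedence: liver worsening is defined by laboratory tests, so that would largely cancel the exemption for this organ. With last visit planned for June 2020 and the SAP's response algorithm dated 19 October 2020, the table is probably the only practical change.
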